6.5.2 Laboratory Parameters

Laboratory assessments will include:

Biochemistry: total protein, gamma glutamyl transferase (GGT), lactate dehydrogenase (LDH), sodium, potassium, chloride, magnesium, glucose, total bilirubin, AST(SGOT), ALT(SGPT), alkaline phosphatase, amylase, albumin, BUN, calcium, creatinine, uric acid, HCO₃, total cholesterol, creatinine phosphokinase, and inorganic phosphorous.

Hematology: RBC count, hemoglobin, hematocrit, platelet count, WBC count, WBC differential.

Urinalysis: Pregnancy, pH (dipstick), specific gravity (dipstick), glucose (dipstick), protein (dipstick), ketones (dipstick), blood (dipstick), Nitrites, Leucocytes and sediment microscopy if indicated by the dipstick.

Laboratory results will be presented in listings in measured units and summaries in conventional units.

Continuous laboratory values will be summarized descriptively by treatment group over time for each visit and as change from baseline to each visit. Categorical laboratory values will be summarized as the number and percentages of subjects in each category by treatment group over time for visit.

Laboratory parameters will also be summarized in shift tables by treatment, to determine the number and percentage of subjects with measurements classified in a particular category at each post-baseline visit with reference to the same classification at baseline. Biochemistry and hematology parameters (which are continuous in nature) will use the classifications of low, normal, and high relative to normal ranges, whereas appropriate categories will be selected for urinalysis parameters (which are categorical in nature), for example, normal and abnormal.

Subjects missing a value at any time point will be excluded from the summary statistics for that time point. If a subject has more than one value at any time point, then the latest non missing value will be used for summarization. All values will be presented in the data listings.

Listings of all individual laboratory data, indicating any values out of the normal range will be produced. A listing of lab parameter values flagged as abnormal will also be provided.

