Table 14.3.4.2	Biochemistry Laboratory Data – Shift from Baseline: Safety Population
Table 14.3.4.3	Hematology Laboratory Data – Observed and Change from Baseline: Safety Population
Table 14.3.4.4	Hematology Laboratory Data – Shift from Baseline: Safety Population
Table 14.3.4.5	Urinalysis Laboratory Data – Observed and Change from Baseline: Safety Population
Table 14.3.4.6.1	Urinalysis Laboratory Data – Shift from Baseline – Numerical Tests: Safety Population
Table 14.3.4.6.2	Urinalysis Laboratory Data – Shift from Baseline – Categorical Tests: Safety Population
Other Safety Assessments	
Table 14.4.1	Vital Signs – Observed and Change from Baseline to Weeks 26 and 52: Safety Population
Table 14.4.2	Uveitis Assessment at Baseline, Week 26 and Week 52: Safety Population

Listings:

Listing Number	Title
Listing 16.2.1.1	Subject Disposition and End of Participation in the Trial: Intent-to-Treat Population
Listing 16.2.1.2	Inclusion and Exclusion Criteria: Intent-to-Treat Population
Listing 16.2.2.1	Major Protocol Deviations: Intent-to-Treat Population
Listing 16.2.2.2	Analysis Populations: Intent-to-Treat Population
Listing 16.2.3.1	Subjects Excluded from Efficacy Analysis
Listing 16.2.4.1	Demographics and Baseline Disease Characteristics: Intent-to-Treat Population
Listing 16.2.4.2	Crohn's Disease History: Intent-to-Treat Population
Listing 16.2.4.3	Medical History (excluding Crohn's disease): Intent-to-Treat Population
Listing 16.2.4.4	Surgical History of Crohn's disease: Intent-to-Treat Population
Listing 16.2.4.5	Prior anti-TNF Agents Use: Intent-to-Treat Population
Listing 16.2.4.6	Prior Alcohol Consumption and Tobacco Use: Intent-to-Treat Population
Listing 16.2.4.7	Prior and Concomitant Medications Use: Intent-to-Treat Population
Listing 16.2.4.8	Prior and Concomitant Steroids Use: Intent-to-Treat Population
Listing 16.2.4.9	Crohn's Disease Prior and Concomitant Medications: Intent-to-Treat Population
Listing 16.2.4.10	Concomitant Procedures: Intent-to-Treat Population
Listing 16.2.5.1	Drug Exposure and Compliance: Intent-to-Treat Population
Listing 16.2.6.1	Crohn's Disease Activity Index (CDAI) Score: Intent-to-Treat Population
Listing 16.2.6.2	Remission, Response and Steroid Free by Time On study: Intent-to-Treat Population
Listing 16.2.6.3	SF-36 Questionnaire Domain and Component Scores: Intent-to-Treat Population
Listing 16.2.6.4	Inflammatory Bowel Disease Questionnaire (IBDQ) Score: Intent-to-Treat Population

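### The latest-value rule can remove abnormal laboratory results from every by-arm count, and no worst post-baseline table restores them; the size is unknown and may be zero

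*SAP*

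**What the plan says.** SAP 6.5.2 (Laboratory Parameters) sets the rule for duplicate values: "If a subject has more than one value at any time point, then the latest non missing value will be used for summarization". It also plans shift tables by arm, which place each subject in a category "at each post-baseline visit with reference to the same classification at baseline". For the continuous tests, meaning chemistry and blood counts, these tables "will use the classifications of low, normal, and high relative to normal ranges".

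Two listings keep the values that the rule sets aside. The section says "All values will be presented in the data listings", and then "A listing of lab parameter values flagged as abnormal will also be provided".

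The table list in SAP 8.1 (Tables 14.3.4.1 to 14.3.4.6.2) contains observed and change-from-baseline tables and shift tables, for example "Hematology Laboratory Data – Shift from Baseline: Safety Population". It names no table of worst post-baseline category, graded toxicity or marked abnormality.

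The visit schedule in SAP 4.1.1 places hematology and biochemistry at 12 post-baseline visits, from Week 2 to Week 56. Neither document says how a repeat or unscheduled test is assigned to a time point.

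**The concern.** A repeat test may be ordered because the previous result was out of range. If so, keeping the last value at a time point selects the recovered value over the one that prompted the repeat. A subject with a high liver enzyme at Week 12 whose same-visit repeat is in range would be tabulated as normal at Week 12.

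Laboratory parameters are stated safety endpoints (SAP 2.2.5), and treatment lasts up to 52 weeks. The shift tables are the only planned by-arm counts of out-of-range results. A value missing from them can still be found in a listing, but it has no numerator, denominator or comparison between arms.

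The rule also differs from the SAP's handling of adverse events. Section 6.5.1 counts a subject at maximum severity and treats missing severity as severe. Nothing in the SAP explains why laboratory data keep the last value, however extreme the earlier one was.

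**Working it through.** The plan states no figure that depends on this rule, so there is nothing to reproduce. The check traces the rule through the planned outputs and then gives an illustration.

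**Step 1. Does the rule reach the shift tables?** Yes, on a natural reading. It applies to summarization, and SAP 6.5.2 says laboratory parameters are summarized in shift tables. The unit of those tables is the visit: "to determine the number and percentage of subjects with measurements classified in a particular category at each post-baseline visit".

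**Step 2. What happens to a repeat?** The documents leave two possibilities open.

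| Assignment of the repeat | Repeat in range | Repeat worse than the scheduled value |
|---|---|---|
| Same time point as the scheduled test | Subject counted normal; abnormal value in listings only | Subject counted at the worse value |
| Left unscheduled | Scheduled abnormal value stands | Worse value enters no by-visit table |

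Each assignment therefore has a case in which the more abnormal result is missing from the by-visit counts.

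**Step 3. Does another table restore the count?** No. The observed and change tables follow the same rule, and the listings are by subject. The baseline rule in SAP 6.1.4 (last non-missing result before first dose) concerns pre-dose values only.

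**Step 4. Size, by assumption.** Let a be the share of subjects abnormal on the first test at a visit, q the share of those repeated at the same time point, and n the share of those repeats in range. Leaving aside subjects whose first value is normal and whose repeat is abnormal:

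- tabulated rate = a × (1 − q × n)
- relative understatement = q × n

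None of a, q or n is in the documents. Take a = 10% and 162 subjects per arm (SAP 6.1.9; the safety population may be slightly smaller). The count based on the first value is 162 × 0.10 = 16.2.

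| q | n | q × n | Subjects tabulated abnormal |
|---|---|---|---|
| 0 | any | 0% | 16.2 |
| 25% | 25% | 6.25% | 15.2 |
| 50% | 50% | 25% | 12.15 |
| 100% | 50% | 50% | 8.1 |
| 100% | 75% | 75% | 4.05 |

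**Step 5. Effect on the comparison.** Assume first-test rates of 10% and 5%.

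- Equal q × n = 25% in both arms: 10% × 0.75 = 7.5% and 5% × 0.75 = 3.75%. The difference falls from 5 to 3.75 percentage points; the ratio stays at 2.
- Equal q × n = 50%: 5% and 2.5%. The difference falls to 2.5 points; the ratio stays at 2.

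The ratio moves only if q × n differs between arms, and the documents give no ground for assuming that it does.

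**The case against.** The strongest objection is that the documents do not establish the mechanism. They do not say what triggers a repeat, how often repeats occur or where they are stored. A reader might infer that the ±7-day windows in SAP 4.1.1 pull repeats into the same visit. Those are windows for when a scheduled visit may take place (±3 days at Weeks 2 to 6), not analysis windows that map unscheduled tests. If repeats are held as unscheduled, the scheduled abnormal value stands and the understatement is zero. This objection stands: it rules out any claim that the tables will understate toxicity by a given amount.

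A second objection is that other safeguards reduce the consequence. With 12 post-baseline draws, sustained toxicity should reappear at later visits, so single transient excursions are the ones at risk. Abnormal values are listed, the DSMB reviews laboratory findings at three planned meetings (SAP 6.6), and adverse events are tabulated by arm. A result that normalizes on repeat may also have been spurious. These points limit the consequence, but none of them supplies a by-arm count of abnormal results.

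Third, the choice of first, latest or worst value within a visit is partly convention. That is fair. It does not answer the lack of any worst post-baseline summary, which matters whichever convention is used.

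**Conclusion.** The point holds as a gap in the plan. The stated rule can remove abnormal results from every by-arm laboratory count, and no planned table puts them back. This rests on reading the shift tables as summaries, which is how SAP 6.5.2 describes them.

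The size is q × n, which is unknown and may be zero. The 0% to 75% range above reflects assumed inputs only.

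Two stronger readings are tempting and unsupported. The first is that the shift tables definitely understate toxicity because repeats follow abnormal results; no passage gives the triggers. The second is that the rule favors RHB-104 in particular. With equal q × n the risk difference shrinks and the risk ratio is unchanged, and the documents do not show that q × n differs by arm. White cell count as an entry criterion adds nothing, since it concerns screening.

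No primary or key secondary efficacy inference is affected. The change is still worth making, because it is cheap and works however repeats are assigned.

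**What to change.** In SAP 6.5.2 and the table list in 8.1:

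1. Add biochemistry and hematology shift tables from baseline to worst post-baseline category, with highest and lowest values handled separately, including repeat and unscheduled values.
2. For by-visit means and shift tables, use the scheduled (first) value instead of the latest.
3. State how repeat and unscheduled tests are assigned to visits.

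The cost is SAP wording and minor programming on data already collected. Reported abnormality rates will be higher in both arms. Because the categories are only low, normal and high, some of the added counts will be minor or transient out-of-range values, which could dilute the contrast between arms in the worst-value table. Retaining the by-visit tables beside it allows that to be judged.

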6.5.3 Vital Signs

Vital signs include the following:

- Supine systolic blood pressure (SBP)
- Supine diastolic blood pressure (DBP)
- Supine pulse rate
- Respiratory rate
- Temperature
- Height
- Weight
- BMI

Vital signs are recorded at baseline and at different visits post-baseline. Actual and change from baseline values will be summarized using descriptive statistics by visit and treatment group. The mean, standard deviation, median, and range will be used to summarize the data. For each subject, vital signs data will be presented in a data listing.

6.5.4 12-Lead ECG

Study investigators will record each subject ECG data. The significance and interpretation of each ECG finding and assessments of the QTc and other ECG intervals will be made by the ECG specialized Lab. All ECG data will be presented in the subject data listings with annotations indicating any abnormal values. For analysis details and presentation of the ECG findings, a specialized independent technical report will be produced by different specialized expert.

6.5.5 Uveitis Assessment

Results from Uveitis assessments will be listed and summarized by treatment and overall as the number and percentage of subjects with Uveitis suspected (yes or no), and if suspected, with Uveitis confirmed (yes or no).

6.6 Data and Safety Monitoring Board (DSMB)

In order to ensure the safety of study participants, a Data Safety Monitoring Board (DSMB) will be established to monitor data on an ongoing basis. The committee will meet periodically to review interim safety data. Following their review, the DSMB will recommend whether the study should continue as is or be modified to improve safety. The DSMB will consist of at least one clinician with experience in the care of patients with inflammatory bowel disease and at least one statistician. The DSMB charter will describe the membership, responsibilities, meeting procedures related to the DSMB, output to be reviewed, and interim analysis rules to be applied. The DSMB at regular intervals will review the following, at each of the safety analyses meetings:

- Demographic and baseline characteristics
- Physical exam, vital signs, clinical laboratory findings, ECG findings
- Summaries of SAE, AEs and deaths
- Summaries of subject withdrawals
- Summaries of subject accrual and retention
- Summaries of protocol violations

The DSMB will carefully consider safety results and then provide a recommendation for continuing or stopping the trial for safety to the Sponsor after each DSMB safety meeting. There are three planned DSMB meetings for the study. The first meeting is planned for when 25% of patients reach 26 weeks of treatment. The second and third meetings are to occur after 50% and 75% of patients have completed 26 weeks of treatment or terminated study participation early. Once the required numbers of patients have reached each of these thresholds, a database snapshot will occur. The DSMB will convene to review safety data within 3 months of the data base snapshot. The timing between each DSMB meeting will be at least 6 months.

In addition, it is anticipated that during the second DSMB meeting, an interim efficacy (or inefficacy) and futility analyses will be performed and the results of this analysis evaluated by the DSMB.

It is prospectively planned as specified in the protocol that the second DSMB meeting at 50% randomized subjects will comprise a formal interim of safety and efficacy (or inefficacy) and futility analyses will be performed and the results of this analysis evaluated by the DSMB.

6.7 Interim Analysis

One prospectively planned interim analysis for safety and futility is planned after 50% (205) patients have completed week 26 of treatment. The DSMB will evaluate the results from this analysis to assess RHB-104 safety, efficacy (or inefficacy), and the feasibility of continuing or stopping the study. The planned interim analysis is designed to have an alpha level of 0.003 as the criteria for stopping the trial early for efficacy or inefficacy based on using the O'Brien-Fleming spending function to determine the test boundaries. For the interim analysis, the Cochran-Mantel-Haenszel (CMH) test will be used to compare treatment groups controlling for the

Final Version 3.0, 05 April 2018

stratification variable (anti-TNF agents (yes/no). The interim test is a 2-sided test ($P=0.003$), meaning that the trial can be stopped if there is overwhelming evidence of efficacy or overwhelming evidence of inefficacy. Further details are provided in the DSMB charter for this study.

The protocol specified α -spending for the prospectively plan interim analysis is 0.003. All tests at the final analysis will be conducted at significance level of $\alpha = 0.049$. The interim analyses will consider subjects with missing 26 week assessments to not be in a state of remission at 26 weeks.

Regarding the interim efficacy (or inefficacy) of the data, recommendations for early termination will be guided by the Lan-DeMets alpha-spending implementation of O'Brien-Fleming spending function to determine the test boundaries. The efficacy boundary preserves the overall 2-sided study alpha level of 0.05. The alpha level at first & second sequential test is 0.003 & 0.049, respectively.

The DSMB will carefully consider the safety and efficacy interim results and then provide a recommendation for continuing or stopping the study. The sponsor and all personnel involved in the conduct of the study will remain blinded to the treatment assigned to each subject. The DSMB will disseminate interim results in a manner that will protect the scientific and ethical aspects of the study. The responsibility of the DSMB, the scope of the data to be reviewed, the organization of the review process, dissemination requirements and procedures are described in DSMB charter.

6.8 Changes to Statistical Analysis Methods Planned in the Protocol

Changes to planned analyses from the protocol will be incorporated in the SAP, if they occur before the unblinding of the database.

7. ADDITIONAL OTHER EXPLOATORY ANALYSES

Other exploratory subgroup analyses to characterize safety and efficacy activities of HRB-104 versus placebo may be conducted. These additional exploratory analyses will be decided at the time of final data analysis.

8. TABLES, LISTINGS, AND FIGURES

The intended layouts for unique summary tables, listings, and figures (TLFs) are presented in a separate document. However, it may be necessary to change the table layouts, as appropriate, upon review of the data available without modifying the SAP text.

8.1 Tables, Listings and Graphs (TLFs) for Study Report

List of Tables and Graphs:

Table Number	Title
Analysis Populations and Disposition	
Table 14.1.1.1	Subject Disposition: All Enrolled Subjects
Table 14.1.1.2	Major Protocol Deviations: Intent-to-Treat Population
Table 14.1.1.3	Major Protocol Deviations: Safety Population (if different from ITT)
Demographics and Baseline Characteristics	
Table 14.1.2.1	Demographics and Baseline Characteristics: Intent-to-Treat Population
Table 14.1.2.2	Demographics and Baseline Characteristics: Safety Population (if different from ITT)
Table 14.1.2.3	Vital Signs at Baseline: Intent-to-Treat Population
Table 14.1.2.4	Physical Examination at Baseline: Intent-to-Treat Population
Medical History	
Table 14.1.3.1	Crohn's Disease History: Intent-to-Treat Population
Table 14.1.3.2	Crohn's Disease Prior Treatments: Intent-to-Treat Population
Prior and Concomitant Medications	
Table 14.1.4.1	Prior Medications Use: Intent-to-Treat Population
Table 14.1.4.2	Concomitant Medications Use: Intent-to-Treat Population
Table 14.1.4.3	Prior anti-TNF Agents Use: Intent-to-Treat Population
Table 14.1.4.4	Crohn's Disease Concomitant Medications Use: Intent-to-Treat Population
Table 14.1.4.5	Prior Steroids Use: Intent-to-Treat Population
Table 14.1.4.6	Concomitant Steroids Use: Intent-to-Treat Population
Table 14.1.4.7	Crohn's Disease Concomitant Steroids Use: Intent-to-Treat Population
Table 14.1.4.8	Prior Immunomodulators Use: Intent-to-Treat Population
Table 14.1.4.9	Concomitant Immunomodulators Use: Intent-to-Treat Population
Treatment Exposure and Compliance	
Table 14.1.5.1	Study Drug Exposure: Intent-to-Treat Population
Table 14.1.5.2	Treatment Compliance: Intent-to-Treat Population
Primary Efficacy Endpoint	
Table 14.2.1.1	Primary Objective – Remission Week 26: Intent-to-Treat Population

Table 14.2.1.2	Sensitivity Analysis: Remission Week 26: Modified intent-to-Treat Population
Table 14.2.1.3	Sensitivity Analysis: Remission Week 26: Per-protocol Population
Table 14.2.1.4	Sensitivity Analysis: Remission Week 26: Completers Analysis (Observed Cases)
Table 14.2.1.5	Exploratory: Remission Week 26 by Treatment Group for Each Baseline Subgroup from Logistic Regression analysis: Intent-to-Treat Population
Figure 14.2.1.1	Exploratory: Remission Week 26 Forest Plots by Treatment Group for Each Baseline Subgroup Analysis: Intent-to-Treat Population
Key Secondary Efficacy Endpoints	
Table 14.2.2.1.1	Response Week 26: Intent-to-Treat Population
Table 14.2.2.1.2	Sensitivity Analysis - Response Week 26: Modified Intent-to-Treat Population
Table 14.2.2.1.3	Sensitivity Analysis - Response Week 26: Per-protocol Population
Table 14.2.2.1.4	Sensitivity Analysis - Response Week 26: Completers Analysis (Observed Cases)
Table 14.2.2.1.5	Exploratory: Response Week 26 by Treatment Group for Each Baseline Subgroup from Logistic Regression analysis: Intent-to-Treat Population
Figure 14.2.2.1.1	Exploratory: Response Week 26 Forest Plots by Treatment Group for Each Baseline Subgroup Analysis: Intent-to-Treat Population
Table 14.2.2.1.6	Sensitivity Analysis – Mixed Model Repeat Measures (MMRM) of CDAI Score: Intent-to-Treat Population
Table 14.2.2.1.7	Sensitivity Analysis – Mixed Model Repeat Measures (MMRM) of CDAI Score Change from Baseline: Intent-to-Treat Population
Table 14.2.2.1.8	Sensitivity Analysis – Negative Binomial Generalized Model Analysis of CDAI Remission: Intent-to-Treat Population
Table 14.2.2.1.9	Sensitivity Analysis – Poisson Generalized Model Analysis of CDAI Remission: Intent-to-Treat Population
Figure 14.2.2.1.6	Sensitivity Analysis – Mixed Model Repeat Measures (MMRM) of CDAI Score – Plot of Least Square Mean CDAI Score with 95% CI over time: Intent-to-Treat Population
Table 14.2.2.2.1	Remission Week 52: Intent-to-Treat Population
Table 14.2.2.2.2	Sensitivity Analysis - Remission Week 52: Modified Intent-to-Treat Population
Table 14.2.2.2.3	Sensitivity Analysis - Remission Week 52: Per-protocol Population
Table 14.2.2.2.4	Sensitivity Analysis - Remission Week 52: Completers Analysis (Observed Cases)
Table 14.2.2.2.5	Exploratory: Remission Week 52 by Treatment Group for Each Baseline Subgroup from Logistic Regression analysis: Intent-to-Treat Population
Figure 14.2.2.2.1	Exploratory: Remission Week 52 Forest Plots by Treatment Group for Each Baseline Subgroup Analysis: Intent-to-Treat Population
Table 14.2.2.3.1.1	Durable (Sustained) Remission Week 26 through Week 52: Intent-to-Treat Population
Table 14.2.2.3.1.2	Complementary Analysis: Proportion of subjects that maintained durable remission at least 3 out of the 4 visits assessed (i.e. $\geq 75\%$ of the visits in

	remission) week 26 through week 52: Intent-to-Treat Population
Table 14.2.2.3.2	Sensitivity Analysis – Durable Remission Week 26 through Week 52: Modified Intent-to-Treat Population
Table 14.2.2.3.3	Sensitivity Analysis – Durable Remission Week 26 through Week 52: Per-protocol Population
Table 14.2.2.3.4	Sensitivity Analysis - Durable Remission Week 26 through Week 52: Completers Analysis (Observed Cases)
Table 14.2.2.3.5	Exploratory: Durable Remission Week 26 through Week 52 by Treatment Group for Each Baseline Subgroup from Logistic Regression analysis: Intent-to-Treat Population
Figure 14.2.2.3.1	Exploratory: Durable Remission Week 26 through Week 52 Forest Plots by Treatment Group for Each Baseline Subgroup Analysis: Intent-to-Treat Population
Table 14.2.2.4.1	Early Remission Week 16: Intent-to-Treat Population
Table 14.2.2.4.2	Sensitivity Analysis – Early Remission Week 16: Modified Intent-to-Treat Population
Table 14.2.2.4.3	Sensitivity Analysis - Early Remission Week 16: Per-protocol Population
Table 14.2.2.4.4	Sensitivity Analysis - Early Remission Week 16: Completers Analysis (Observed Cases)
Table 14.2.2.4.5	Exploratory: Early Remission Week 16 by Treatment Group for Each Baseline Subgroup from Logistic Regression analysis: Intent-to-Treat Population
Figure 14.2.2.4.1	Exploratory: Early Remission Week 16 Forest Plots by Treatment Group for Each Baseline Subgroup Analysis: Intent-to-Treat Population
Table 14.2.2.5.1	Steroid Free Remission Week 52: Intent-to-Treat
Table 14.2.2.5.2	Sensitivity Analysis – Steroid Free Remission Week 52: Modified Intent-to-Treat Population
Table 14.2.2.5.3	Sensitivity Analysis - Steroid Free Remission Week 52: Per-protocol Population
Table 14.2.2.5.4	Sensitivity Analysis - Steroid Free Remission Week 52: Completers Analysis
Table 14.2.2.5.5	Exploratory: Steroid Free Remission Week 52 by Treatment Group for Each Baseline Subgroup from Logistic Regression analysis: Intent-to-Treat Population
Figure 14.2.2.5.1	Exploratory: Steroid Free Remission Week 52 Forest Plots by Treatment Group for Each Baseline Subgroup Analysis: Intent-to-Treat Population
Supportive/Supplementary Endpoints: Time-to-Event Endpoints	
Table 14.2.3.1.1	Time to Remission: Intent-to-Treat Population
Table 14.2.3.1.2	Duration of Remission: Intent-to-Treat Population
Table 14.2.3.1.3	Time to Response: Intent-to-Treat Population
Table 14.2.3.1.4	Duration of Response: Intent-to-Treat Population
Figure 14.2.3.1.1	Time to Remission Kaplan Meir Survival Curve: Intent-to-Treat Population
Figure 14.2.3.1.2	Duration of Remission Kaplan Meir Survival Curve: Intent-to-Treat Population
Figure 14.2.3.1.3	Time to Response Kaplan Meir Survival Curve: Intent-to-Treat Population
Figure 14.2.3.1.4	Duration of Response Kaplan Meir Survival Curve: Intent-to-Treat Population
Supportive/Supplementary Endpoints: Remission and Response Endpoints	

Table 14.2.3.2.1.1	Sustained Remission Week 16 through Week 52: Intent-to-Treat Population
Table 14.2.3.2.1.2	Complementary Analysis: Proportion of subjects that maintained durable remission at least 5 out of the 6 visits assessed (i.e. $\geq 83\%$ of the visits in remission) week 16 through week 52: Intent-to-Treat Population
Table 14.2.3.2.2	Early Response Week 16: Intent-to-Treat Population
Table 14.2.3.2.3	Response week 52: Intent-to-Treat Population
Supportive/Supplementary Endpoints: Endoscopic Assessments	
Table 14.2.3.3.1	Baseline and Change from Baseline to Weeks 26 in CDEIS Scores: Intent-to-Treat Population
Table 14.2.3.3.2	Baseline and Change from Baseline to Weeks 26 in SES-CD Scores: Intent-to-Treat Population
Table 14.2.3.3.3	Endoscopic Remission based on CDEIS score week 26: Intent-to-Treat Population
Table 14.2.3.3.4	Endoscopic Remission based on SES-CD scores: Intent week 26-to-Treat Population
Table 14.2.3.3.5	Shift from Remission to No Remission and Vice Versa based on CDEIS scores Week 26 by Treatment Group: Intent-to-Treat Population
Table 14.2.3.3.6	Shift from Remission to No Remission and Vice Versa based on SES-CD scores Week 26 by Treatment Group: Intent-to-Treat Population
Table 14.2.3.3.7	Endoscopic Response: 50% reduction in CDEIS scores from baseline to week 26: Intent-to-Treat Population
Table 14.2.3.3.8	Endoscopic Response: 50% reduction in SES-CD scores from baseline to week 26: Intent-to-Treat Population
Table 14.2.3.3.9	Endoscopic Response: 25% reduction in CDEIS scores from baseline week 26: Intent-to-Treat Population
Table 14.2.3.3.10	Endoscopic Response: 25% reduction in SES-CD scores from baseline week 26: Intent-to-Treat Population
Table 14.2.3.3.11	Correlations CDEIS, SES-CD & CDAI Week 26: Intent-to-Treat Population
Figure 14.2.3.3.1	Scatter Plot: CDEIS Total Score vs. CDAI Total score baseline, weeks 26: Intent-to-Treat Population
Figure 14.2.3.3.2	Scatter Plot: SES-CD Total Score vs. CDAI Total score baseline, weeks 26: Intent-to-Treat Population
Supportive/Supplementary Endpoints: Inflammation Assessment	
Table 14.2.3.4.1	Summary Serum Marker of Inflammation (CRP) Level: Intent-to-Treat Population
Table 14.2.3.4.2	Summary Stool Marker of Inflammation Level - Fecal calprotectin: Intent-to-Treat Population
Table 14.2.3.4.3	Proportion of subjects with CRP Marker of Inflammation Normal/High by Visit by Treatment : Intent-to-Treat Population
Table 14.2.3.4.4	Proportion of subjects with Fecal calprotectin Normal/High by Visit by Treatment : Intent-to-Treat Population
Table 14.2.3.4.5	Shift in Serum Marker of Inflammation (CRP) Status Normal/High Baseline to

	Week 26 and Week 52: Intent-to-Treat Population
Table 14.2.3.4.6	Shift in Stool Marker of Inflammation (Fecal calprotectin) Status Normal/High Baseline to Week 26 and Week 52 : Intent-to-Treat Population
Figure 14.2.3.4.1	Scatter Plot: CRP vs. CDAI Total score baseline, weeks 26 & 52: Intent-to-Treat Population
Figure 14.2.3.4.2	Scatter Plot: Fecal calprotectin vs. CDAI Total score baseline, weeks 26 & 52: Intent-to-Treat Population
Supportive/Supplementary Endpoints: Quality of Life Assessment	
Table 14.2.3.5.1	Short Form (SF-36) questionnaire total score and domain scores at Baseline, Week 26 and Week 52: Intent-to-Treat Population
Table 14.2.3.5.2	Inflammatory Bowel Disease Questionnaire (IBDQ) Score at Baseline, Week 26 and Week 52: Intent-to-Treat Population
Figure 14.2.3.5.1	Bar Graphs of SF-36 Total Score and Domain Scores at Baseline, 26 and 52 Weeks by treatment group: Intent-to-Treat Population
Figure 14.2.3.5.2	Bar Graphs of IBDQ Score at Baseline, 26 and 52 weeks by Treatment group: Intent-to-Treat Population
Exploratory Endpoints: MAP Detection	
Table 14.2.4.1.1	Baseline and Change in MAP Blood PCR Assay Status After Weeks 26 and 52: Intent-to-Treat Population
Table 14.2.4.1.2	Baseline and Change in Blood Culture Status After Weeks 26 and 52: Intent-to-Treat Population
Table 14.2.4.1.3	Baseline and Change in MAP Colon Biopsy PCR Assay Status After Weeks 26 and 52: Intent-to-Treat Population
Table 14.2.4.2.1	Shift in MAP Blood PCR Assay Status From Baseline to Weeks 26 and 52: Intent-to-Treat Population
Table 14.2.4.2.2	Shift in Blood Culture Status From Baseline to Weeks 26 and 52: Intent-to-Treat Population
Table 14.2.4.2.3	Shift in Colon Biopsy PCR Assay Status From Baseline to Weeks 26 and 52: Intent-to-Treat Population
Table 14.2.4.3.1	Baseline Correlations Blood PCR Assay, Blood Culture Test, Colon Biopsy PCR Assay and CDAI: Intent-to-Treat Population
Table 14.2.4.3.2	Week 26 Correlations Blood PCR Assay, Blood Culture Test, Colon Biopsy PCR Assay and CDAI: Intent-to-Treat Population
Table 14.2.4.3.3	Week 52 Correlations Blood PCR Assay, Blood Culture Test, Colon Biopsy PCR Assay and CDAI: Intent-to-Treat Population
Figure 14.2.4.1.1	Scatter Plot: Blood PCR Assay Level vs. CDAI Total score baseline, weeks 26 & 52: Intent-to-Treat Population
Figure 14.2.4.1.2	Scatter Plot: Blood Culture Test vs. CDAI Total score baseline, weeks 26 & 52: Intent-to-Treat Population
Figure 14.2.4.1.3	Scatter Plot: Colon Biopsy PCR Assay vs. CDAI Total score baseline, weeks 26 & 52: Intent-to-Treat Population
Exploratory Endpoints: General Other Endpoints	
Table 14.2.5.1	Proportion of subjects tapered off steroids in each treatment arm by Visit Time

	Points Post Baseline
Table 14.2.5.2	Summary Tissue Levels of Active Agents of RHB-04 in Colon Biopsy Samples by Visit Sample Time-Points Post-baseline
Adverse Events	
Table 14.3.1.1	Adverse Events Incidence Summary: Safety Population
Table 14.3.1.2	Treatment-Emergent Adverse Events by System Organ Class and Preferred Term: Safety Population
Table 14.3.1.3	Treatment-Emergent Adverse Events by System Organ Class, Preferred Term, and Relationship to Study Medication: Safety Population
Table 14.3.1.4	Treatment-Emergent Adverse Events by System Organ Class, Preferred Term, and Maximum Severity: Safety Population
Table 14.3.1.5	Treatment-Emergent Adverse Events Leading to Study Discontinuation by System Organ Class and Preferred Term: Safety Population
Table 14.3.1.6	Treatment-Emergent Serious Adverse Events by System Organ Class and Preferred Term: Safety Population
Table 14.3.1.7	Treatment-Emergent Serious Adverse Events by System Organ Class, Preferred Term, and Maximum Relationship to Study Drug: Safety Population
Table 14.3.2.1	Listing of Subjects with Adverse Events that Led to Death: Safety Population
Table 14.3.2.2	Listing Subjects with Treatment-Emergent Serious Adverse Events: Safety Population
Table 14.3.2.3	Listing Subjects with Adverse Events that Led to Study Discontinuation or Study Drug Interruption: Safety Population
Table 14.3.2.4	Listing of Subjects with Treatment-Emergent Adverse Events Related to Study Drug: Safety Population
Table 14.3.2.5	Listing of Deaths: Safety Population
Labs Assessments	
Table 14.3.4.1	Biochemistry Laboratory Data – Observed and Change from Baseline: Safety Population
Table 14.3.4.2	Biochemistry Laboratory Data – Shift from Baseline: Safety Population
Table 14.3.4.3	Hematology Laboratory Data – Observed and Change from Baseline: Safety Population
Table 14.3.4.4	Hematology Laboratory Data – Shift from Baseline: Safety Population
Table 14.3.4.5	Urinalysis Laboratory Data – Observed and Change from Baseline: Safety Population
Table 14.3.4.6.1	Urinalysis Laboratory Data – Shift from Baseline – Numerical Tests: Safety Population
Table 14.3.4.6.2	Urinalysis Laboratory Data – Shift from Baseline – Categorical Tests: Safety Population
Other Safety Assessments	
Table 14.4.1	Vital Signs – Observed and Change from Baseline to Weeks 26 and 52: Safety Population
Table 14.4.2	Uveitis Assessment at Baseline, Week 26 and Week 52: Safety Population

Listings:

Listing Number	Title
Listing 16.2.1.1	Subject Disposition and End of Participation in the Trial: Intent-to-Treat Population
Listing 16.2.1.2	Inclusion and Exclusion Criteria: Intent-to-Treat Population
Listing 16.2.2.1	Major Protocol Deviations: Intent-to-Treat Population
Listing 16.2.2.2	Analysis Populations: Intent-to-Treat Population
Listing 16.2.3.1	Subjects Excluded from Efficacy Analysis
Listing 16.2.4.1	Demographics and Baseline Disease Characteristics: Intent-to-Treat Population
Listing 16.2.4.2	Crohn's Disease History: Intent-to-Treat Population
Listing 16.2.4.3	Medical History (excluding Crohn's disease): Intent-to-Treat Population
Listing 16.2.4.4	Surgical History of Crohn's disease: Intent-to-Treat Population
Listing 16.2.4.5	Prior anti-TNF Agents Use: Intent-to-Treat Population
Listing 16.2.4.6	Prior Alcohol Consumption and Tobacco Use: Intent-to-Treat Population
Listing 16.2.4.7	Prior and Concomitant Medications Use: Intent-to-Treat Population
Listing 16.2.4.8	Prior and Concomitant Steroids Use: Intent-to-Treat Population
Listing 16.2.4.9	Crohn's Disease Prior and Concomitant Medications: Intent-to-Treat Population
Listing 16.2.4.10	Concomitant Procedures: Intent-to-Treat Population
Listing 16.2.5.1	Drug Exposure and Compliance: Intent-to-Treat Population
Listing 16.2.6.1	Crohn's Disease Activity Index (CDAI) Score: Intent-to-Treat Population
Listing 16.2.6.2	Remission, Response and Steroid Free by Time On study: Intent-to-Treat Population
Listing 16.2.6.3	SF-36 Questionnaire Domain and Component Scores: Intent-to-Treat Population
Listing 16.2.6.4	Inflammatory Bowel Disease Questionnaire (IBDQ) Score: Intent-to-Treat Population
Listing 16.2.6.5	Inflammation Parameters: Intent-to-Treat Population
Listing 16.2.6.6	MAP Detection (yes/no): Intent-to-Treat Population
Listing 16.2.6.7	Endoscopic Assessment – CDEIS: Intent-to-Treat Population
Listing 16.2.6.8	Endoscopic Assessment – SES-CD: Intent-to-Treat Population
Listing 16.2.6.9	MAP Assessment – Blood PCR Assay
Listing 16.2.6.10	MAP Assessment – Blood Culture
Listing 16.2.6.11	MAP Assessment – Colon Biopsy
Listing 16.2.6.12	Inflammation Assessment – CRP marker
Listing 16.2.6.13	Inflammation Assessment – Fecal calprotectin
Listing 16.2.7.1	Adverse Events: Safety Population
Listing 16.2.8.1	Laboratory Assessments -: Biochemistry: Safety Population
Listing 16.2.8.2	Laboratory Assessments – Hematology: Safety Population
Listing 16.2.8.3	Laboratory Assessments - Urinalysis: Safety Population
Listing 16.2.9.1	Stool Samples - C. Difficile Toxin: Safety Population
Listing 16.2.9.2	Urine Pregnancy Test: Safety Population

STATISTICAL ANALYSIS PLAN

RedHill Biopharma Ltd.

RHB-104-01

Page 50

Listing 16.2.9.3	Uveitis Assessment: Safety Population
Listing 16.2.9.4.1	12-Lead ECG (Part 1): Safety Population
Listing 16.2.9.4.2	12-Lead ECG (Part 2): Safety Population
Listing 16.2.9.4.3	12-Lead ECG (Part 3): Safety Population
Listing 16.2.9.5	Vital Signs: Safety Population
Listing 16.2.9.6.1	Physical Examination at Screening: Safety Population
Listing 16.2.9.6.2	Physical Examination Significant Change from Previous Visit: Safety Population

